9.5 STUDY SIZE

In 2008~2013 NHI database, approximately 200,000 patients per year with COPD were diagnosed using COPD diagnostic code and a prescription for COPD medications (LAMA, LABA, ICS + LABA, SAMA, SABA, SAMA + SABA, PDE-4, systemic beta agonist, theophylline). In COPD patients, the use of LAMA and ICS/LABA was 26 to 37%, respectively. We expect the study to include a minimum of 5,000 patients per arm, a conservative estimate.

9.6 DATA MANAGEMENT

We will collect the data from the medical insurance claims from the Korean National Health Insurance (NHI) claims database, which will be provided for research purposes by the Korean NHIC with strict confidentiality guidelines All analyses were performed with SAS and R .

Data for this study will be obtained via the following sources:

- Eligibility DB
 - Sociodemo-graphics variables : sex, age, residential area, insurance type (the employee insured, the self-employed insured, dependants, medical aid), monthly contributions, occupation
 - Vital statistics : dates of birth and death, cause of death (ICD-10 codes)
- Health care utilization DB
 - Diagnosis : International Classification of Disease-10 codes (main disease code, sub disease code)
 - Utilization and cost : date of visit, types of medical institutions (clinics/hospitals/tertiary hospitals/public health centres), types of visit (inpatient/outpatient/emergency/intensive care), length of stay, medical cost (insurer/patient), et al.
 - Health care procedures and medications : Operation and procedure codes, medication history (generic name code, dose, duration of prescription), material codes, et al.

Data is extracted from the NHIS and stored on a secured, shared server for statistical analyses. The original data will be stored in its own, read-only directory to protect the integrity of the extracted data. After obtaining an approval from the NHIS, data analysts can access the data and conduct analysis in a secured computer. NHIS's policy strictly forbids exportation of the original data, however, results obtained from statistical analyses can be exported after an internal review.

9.7 DATA ANALYSIS

The study population consists of COPD patients that have received LAMA and ICS/LABA treatment. The study consists of three stages: a) identification and extraction of LAMA-exposed and ICS/LABA-

exposed cohort, b) matching between LAMA-exposed and ICS/LABA-exposed and c) descriptive analysis of cohorts and analysis of outcomes.

Detailed methodology for summary and statistical analyses of data generated in this study will be documented in an SAP. The SAP may modify the plans outlined in the protocol; any major modifications of primary endpoint definitions or their analyses would be reflected in a protocol amendment.

For the purpose of this study, analyses will be conducted using SAS statistical software and R. To address the imbalance of potential confounders between LAMA ICS/LABA groups, we matched treatment groups using propensity scores estimated as by multiple logistic regression analysis *based on* as age, sex, socioeconomics status, *Charlson Comorbidity Index*, and asthma, history of COPD exacerbation. Demographics and clinical characteristics will be tabulated. Frequencies and percentages will be presented for categorical variables. For continuous variables, means, standard deviations, and ranges, or medians and inter-quartile ranges, will be reported as appropriate. We used a standardised difference to compare baseline characteristics between COPD patients who were treated with LAMA and those treated with ICS/LABA. The matched Cox proportional hazards regression analyses will be used to estimate hazard ratios (HRs) HRs and 95% confidence intervals (95% CIs) for all outcomes. For (possibly) repeating events (such as *exacerbation event*) *additionally* a Poisson regression model will be fitted for the number of events (taking into account the matching). The cox and Poisson models will be adjusted for unbalanced PS-variables at baseline. Mortality was estimated by the Kaplan-Meier method, and results were compared between groups using the log-rank test.

9.7.1 Analysis Dataset : Patients selection

The matching between LAMA[Spriva® HandiHaler® Respimat® (Tiotropium Bromide Monohydrate)] and ICS/LABA are performed by sex, age category (5 year spans above 55 years), years since diagnosis of COPD, as available in the database, and propensity score.

9.7.1.1 Propensity score methodology

The propensity score will model the likelihood among COPD patients of receiving LAMA and ICS/LABA. The model for the propensity score will to the extent possible include the following elements:

- 1) Age and sex
- 2) Socioeconomic status (e.g. income, educational level, single living)
- 3) History of COPD exacerbation
- 4) Charlson Comorbidity Index
- 5) History of asthma

A logistic regression analysis will be performed on the identified COPD patients where treatment with LAMA and ICS/LABA groups is the dependent, dichotomous variable and the independent variables are listed above (age, sex and history of COPD exacerbation et al.). Based on this analysis, the propensity score is calculated for each patient. For subgroup analyses, PS matching and evaluation of its success, as presented below, will be re-done as covariate balance is not automatically maintained in sub-cohorts.

Smoking may be an important confounder in COPD but smoking status is usually not available in the databases at all. If smoking status is confirmed to be available, the data will be analysed with and without smoking status included in the model and the magnitude of the confounding effect assessed (sensitivity analysis).

PS matching will be done in a 1:1 ratio using the nearest-neighbor algorithm, using calipers of width equal to 0.2 of the standard deviation of the logit of the PS (matches of the main exposure sub-cohort and the comparator sub-cohort are formed if the caliper width is not exceeded for the logit of PS). For LAMA-exposed patient to ICS/LABA-exposed patients will be selected within the same matching interval of the propensity score. The distribution of propensity scores will be examined between LAMA-exposed and eligible ICS/LABA-exposed. In the matching procedure, matched comparator sub-cohort patients (ICS/LABA) will be removed from the pool of eligible patients among the comparator sub-cohort so that a matched patient is no longer available for consideration as a potential match for another exposed patient.

Evaluation of the success of the matching procedure will be based on a standardized difference (detailed below) of a covariate that is less than 0.1 between treatment groups. A standardized difference of a covariate of less than 0.1 between treatment groups in this study indicates a negligible difference in the mean or prevalence of the covariate. If larger standardized differences than 0.1 for some covariates exist after matching, they will be used in post-matching adjustments (i.e. PS-variables with standardized difference >0.1 will be adjusted for in the analyses). Further adjustments can also be made as appropriate in additional models. Based on differences identified through exploratory analysis of baseline variables, we matched individual patients from each cohort (1:1) to ensure comparison of similar patients.

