9.3.3 Covariates

Age, sex and history of COPD exacerbation, income status(quartile) or medical health insurance are all matching factors and will thus inherently be accounted for.

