9.7.2 Main analysis

For the primary effectiveness outcomes incidence rates (events per 1,000patients-years) with corresponding 95% confidence intervals (CI) will be calculated. This will be evaluated by a matched Cox proportional hazards regression model for counting processes, which allow the follow-up time to be divided into several periods and therefore control for baseline and time-dependent covariates, using the full observational period of available data, i.e. up to 11 years of follow up. The Cox proportional hazards regression will take into account the fact that individual matching (1:1) will be performed by considering the exposed patient and his/her matched controls as one stratum and including this as a stratum in the Cox proportional hazards model. Additional variables will be included in the model if available. The cumulative incidence plots will be accompanied by number of patients at risk at different time points during follow-up. For (possibly) repeating events (such as exacerbation event) additionally a Poisson regression model will be fitted for the number of events (taking into account the matching). Time in the study will be included as an offset variable in the model. The cox and Poisson models will be adjusted for unbalanced PS-variables at baseline.

The outcome will be analyzed separately for each:

- 1) Primary outcome
 - Comparison of pneumonia incidence in COPD patients using LAMA and ICS/LABA
 - Comparison of exacerbations frequency and rate in COPD patients using LAMA and ICS/LABA : moderate or severe exacerbation

Proprietary confidential information © 2022 Boehringer Ingelheim International GmbH or one or more of its affiliated companies

[figure not shown]
- Comparison of time to start triple combination therapy (time from initial 'LAMA mono' or ICS+LABA' to 'LAMA+LABA+ICS' combination) in COPD patients using LAMA and ICS/LABA

2) Secondary outcome

- Comparison of all-cause mortality differences in COPD patients using LAMA and ICS/LABA
- Comparison of lung cancer incidence in COPD patients using LAMA and ICS/LABA
- Comparison of health care utilization: Medical cost / No. of prescriptions, visits and hospitalizations (hospitalization mainly due to severe exacerbation of COPD)

Health care utilization

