9.12 BIAS

This study will include users of LAMA and ICS/LABA. Immortal time bias will be minimal, as the follow-up will begin at the initiation of drug use. Adherence to drug use will be unknown.

Comparing the outcomes between users of LAMA and ICS/LABA will decrease confounding by indication, as the comparison group will have a similar indication to drug use than the patients in the LAMA-exposed cohorts.

The compared sub-cohorts will be matched on the basis of PS. The PS will be computed on the basis of a wide range of covariates related to sociodemographic characteristics, history of exacerbation, other comorbidities, and prior/concomitant use of other drugs. The PS matching will decrease the systematic differences between the sub-cohorts and, thus, decrease confounding.

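### The propensity score list names no prior pneumonia, no calendar year of index and no drug variable, although section 9.12 says the score covers drug use

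*Combined protocol and SAP*

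**What the plan says.** Section 9.7.1.1 introduces its list with "The model for the propensity score will to the extent possible include the following elements" and gives five items: age and sex, socioeconomic status, history of COPD exacerbation, Charlson Comorbidity Index and history of asthma. For the logistic model it adds that "the independent variables are listed above (age, sex and history of COPD exacerbation et al". The abstract and section 9.7 repeat the same set.

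Two other sections name matching factors. In 9.7.1 the matches "are performed by sex, age category (5 year spans above 55 years), years since diagnosis of COPD, as available in the database", together with the score. In 9.3.3, age, sex, exacerbation history and income or insurance status "are all matching factors and will thus inherently be accounted for".

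Section 9.12 describes a broader score. Besides sociodemographic factors and exacerbation history, it names "other comorbidities, and prior/concomitant use of other drugs".

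After matching, 9.7.1.1 requires that "PS-variables with standardized difference >0.1 will be adjusted for in the analyses". Two further clauses are open-ended: "Further adjustments can also be made as appropriate in additional models" (9.7.1.1) and "Additional variables will be included in the model if available" (9.7.2).

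**The concern.** Matching on a score balances the variables in it. A variable left out is balanced only as far as the listed ones stand in for it. Three candidates are missing from every visible list:

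- **Prior pneumonia.** Pneumonia is a primary outcome, and section 7 rests the study on the link between ICS and pneumonia. A prescriber aware of that link could weigh a past pneumonia when choosing between the arms.
- **Calendar year of index.** Initiation spans more than 11 years, over which prescribing, coding, event rates and costs may drift.
- **Drug use.** 9.12 cites it when arguing that the score reduces confounding, but the list has no drug item.

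If any of these differs between arms after matching and also predicts the outcome, the hazard ratios are biased, and more patients will not help. Smoking, by contrast, is described in 9.7.1.1 as usually unavailable. Diagnosis, date and prescription fields are all in the claims source (9.6, Appendix Table 1).

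**Working it through.** The plan states no figure on this point, so there is none to reproduce. Steps 1 to 3 compare the text. Steps 4 and 5 give scale from assumed inputs.

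**1. Lists side by side**

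| Place | Prior pneumonia | Index year | Drug use |
|---|---|---|---|
| Abstract, 9.7, 9.7.1.1 (score) | no | no | no |
| 9.7.1 (direct matching) | no | no (years since diagnosis only) | no |
| 9.3.3 (covariates) | no | no | no |
| 9.12 (description of score) | only if meant by other comorbidities | no | yes |

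Years since diagnosis measures disease duration. Two patients two years after diagnosis can start treatment in 2006 and in 2015. Exacerbation history overlaps with pneumonia only in part: 9.3.2.1 defines exacerbation by a COPD code plus a steroid and/or antibiotic, and pneumonia by separate codes.

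**2. Reach of the balance rule.** The 0.1 threshold triggers adjustment for score variables only, and 9.7 and 9.7.2 repeat that limit. A variable outside the score cannot trigger it. The two open-ended clauses name no variable.

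**3. What the exclusions remove.** Ipratropium (9.2), ICS, leukotriene antagonists and LABA/LAMA combinations are excluded without dates. Patients are also meant to have had no earlier inhaler, and the abstract adds short-acting bronchodilators. What remains is mainly theophylline, systemic beta agonists and PDE-4 inhibitors. Section 9.5 counts these as COPD medications, and 9.2 does not name them.

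**4. Size under assumed inputs.** A simulation used 200,000 patients and 1:1 greedy nearest-neighbour matching without replacement, with the plan's caliper of 0.2 SD of the logit. The listed covariates were assumed to give a logit SD of 0.6.

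*Prior pneumonia*, assumed prevalence 10%, matched on listed covariates only. Residual standardized difference:

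| Odds ratio for arm | Correlation 0 with listed covariates | Correlation 0.6 |
|---|---|---|
| 1.25 | 0.058 | 0.067 |
| 1.5 | 0.132 | 0.108 |
| 2.0 | 0.203 | 0.183 |

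Bias factor = (1 + p1(RR−1)) / (1 + p0(RR−1)), where p1 and p0 are the matched prevalences and RR is the assumed effect on the event rate (2 to 4).
- Smallest: p1 = 0.109, p0 = 0.091, RR 2 gives 1.109/1.091 = 1.016.
- Largest: p1 = 0.135, p0 = 0.074, RR 4 gives 1.405/1.222 = 1.150 (1.152 from unrounded prevalences).
- The same prevalences with RR 3 give 1.270/1.148 = 1.106.

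*Index year*, uniform over 11.33 years, assumed log-odds for arm of 0.03, 0.06 and 0.10 per year. Residual standardized differences are 0.094, 0.208 and 0.326, or 0.31, 0.68 and 1.06 years. Bias factor = (1 + yearly trend in event rate)^years: 1.02^0.31 = 1.006 up to 1.10^1.06 = 1.106.

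With the variable in the score, the residual standardized difference is at most 0.011 in both cases.

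**5. Scale against sampling error.** Section 9.5 gives 5,000 per arm. Assumed: event rate λ = 0.05 and mortality 0.06 per year, uniform accrual over T = 11.33 years, no censoring at discontinuation, hazard ratio near 1.
- Events: with a = 0.05 + 0.06 = 0.11, P = (λ/a)[1 − (1 − e^(−aT))/(aT)] = 0.4545 × 0.4284 = 0.1947. Times 10,000 patients = 1,947 events.
- Informative pairs (first event while both members are at risk, as in the pair-stratified Cox model of 9.7.2): with b = 2a = 0.22, P = 2λ[1/b − 2/(b²T) + 2(1 − e^(−bT))/(b³T²)] = 0.10 × (4.545 − 3.647 + 1.342) = 0.224. Times 5,000 pairs = 1,120.
- SE of the log hazard ratio = 2/√1,120 = 0.060; 1.96 × SE = 0.117; e^0.117 = 1.124, or about ±12%.

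The largest prior-pneumonia shift (odds ratio 2.0 with RR 4) exceeds this half-width. The same case with RR 3 (10.6%) does not, nor does any index-year shift.

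**The case against.** The strongest case against is that the plan leaves room. The list is qualified by feasibility and followed by a loose et al., further adjustment is allowed, variable definitions are deferred to a SAP, and 9.9.4 already concedes residual confounding. This softens the gap but does not close it. The qualifier concerns whether listed items can be included, and the et al. points back to the list. The separate SAP and the redacted section after 9.7.2 cannot be seen, and nothing is claimed about them. The mismatch between 9.12 and 9.7.1.1 needs reconciling in the protocol in any case.

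The second objection is that the size rests wholly on assumptions. That stands. At the low end, the standardized differences (0.058 for prior pneumonia, 0.094 for year) fall below the plan's own threshold of 0.1.

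Three stronger readings are tempting, and the documents do not support them:

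- *That calendar trends are documented.* Section 7 says practice changes slowly. The prescription field added in 2011 (Appendix Table 1) is an administrative identifier and shows no trend in treatment or outcome. Index year is proposed as routine control for a long accrual.
- *That prior long-acting bronchodilator use is uncontrolled for most patients.* That exclusion is dated 2002 to 2005, and 10.33 of the 11.33 accrual years come later. This is a share of calendar time, not of patients, and both versions of the criteria also ask for inhaler-naive patients. The dating is a separate eligibility ambiguity.
- *That the comparison is biased in a known direction.* No passage gives an arm difference for any of the three factors.

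**Conclusion.** The point holds as a gap in the covariate list and an internal inconsistency. No visible list names prior pneumonia, index year or a drug variable; 9.12 claims drug coverage that 9.7.1.1 does not provide; and the mandatory balance rule cannot reach what is outside the score. The textual part needs no assumption. Prior pneumonia has the clearest rationale, because pneumonia is a primary outcome. The drug gap is narrow once the exclusions are counted.

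Direction and size are unknown. The shifts of about 2-15% (prior pneumonia) and 1-11% (index year) depend entirely on the assumed associations in the working. In most of those scenarios the shift is smaller than the confidence interval half-width of about 12%, itself based on assumed event and death rates. It would still be a systematic error that sample size does not remove. The change should be made before analysis; nothing here shows that the planned comparison is invalid.

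**What to change.** Add to the propensity score:

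1. prior pneumonia, for example the ICD-10 codes of 9.3.2.1 recorded before index;
2. calendar year of index;
3. pre-index use of COPD drugs that the exclusions do not remove, mainly theophylline, systemic beta agonists and PDE-4 inhibitors.

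Reconcile 9.12 with 9.7.1.1, and state that drug covariates are measured at or before index only, since use after index can be a consequence of the treatment. Use one covariate list in 9.3.3, 9.7, 9.7.1, 9.7.1.1 and 9.12 (and the abstract). Report standardized differences and apply the 0.1 rule for every variable on it. Separately, reconcile the 2002 to 2005 dating of the long-acting bronchodilator exclusion with the inhaler-naive requirement.

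The cost is protocol and SAP wording plus variables built from fields already held. In the assumed models the matched share falls by 0.1-1.5 percentage points with prior pneumonia in the score and by 0.4-3.3 with index year. Look-back for early initiators must be confirmed, because 9.4 gives data from January 2005 while the exclusions refer to 2002 to 2005.

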9.3.2 Outcomes

9.3.2.1 Primary outcomes

Primary endpoint

- Recorded pneumonia based on 1)ICD-10 code (J12.x-J18.x, J69.0, J84.9, B96.0, J85.1) AND 2) CPT code of chest x-ray(71045-71048) or chest CT(71250,71260,71270,G0297) AND 3) prescription of antibiotics for pneumonia in Korean Guideline) incidence rate per year
- Frequency rate of COPD exacerbation per year
 - Moderate exacerbation: recorded as when COPD patients visited outpatient clinics with an ICD-10 code of COPD and systemic steroid medication and/or antibiotics were prescribed (within the first year after initial prescription of inhalers)
 - Severe exacerbation: when COPD patients visited the emergency room or were admitted to hospital with an ICD-10 code of COPD(*due to COPD worsening*) and were prescribed systemic steroid medication and/or antibiotics (within the first year after initial prescription of inhalers)
- Time to start triple combination therapy ICS/LABA/LAMA)
 - Time to add LAMA in patients with using ICS/LABA or, time to add ICS/LABA in patients with using LAMA before.

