ANNEX 3. ADDITIONAL INFORMATION

Appendix Table 1. List of variables in the NHIS database

DB (number of variables)	Variable name	Details
The eligibility of the insured DB	STND_Y	Standard year for the eligibility of the insured
	PERSON_ID	Personal identification number is replaced by serial number
	SEX	Sex
	AGE_GROUP	Age group at time of diagnosed
	DTH_YM	Year and month of death
	DTH_CODE1	Level 1 (detailed) cause of death
	DTH_CODE2	Level 2 cause of death
	SIDO	Province of residence
	SGG	District of residence
	CTRB_PT_TYPE_CD	Percentile group of income level
The medical treatment DB (called Table 20) [electronic bill of medical treatment]	PERSON_ID	Personal identification number is replaced by serial number
	KEY_SEQ	Key sequence number of claim
	YKIHO_ID	Medical care institution identification number
	RECU_FR_DT	The first day of receiving treatment
	FORM_CD	Form of claimed bill
	DSBJT_CD	Medical subject code
	MAIN_SICK	Main disease code
	SUB_SICK	Sub disease code
	IN_PAT_CORS_TYPE	Route through hospitalization
	OFFC_INJ_TYPE	Type of injuries incurred while on duty

DB (number of variables)	Variable name	Details
	RECN	Days of receiving medical care
	VSCN	Days of visit hospitals or inpatient
	FST_IN_PAT_DT	First date of inpatient
	DMD_TRAMT	Amount of medical expenses based on claims
	DMD_SBRDN_AMT	Expenses paid by beneficiary based on claims
	DMD_JBRDN_AMT	Expenses paid by insurer based on claims
	DMD_CT_TOT_AMT	Total amount for CT based on claims
	DMD_MRI_TOT_AMT	Total amount for MRI based on claims
	EDEC_ADD_RT	Extra rate applied based on claims reviewed
	EDEC_TRAMT	Amount of medical expenses based on claims reviewed
	EDEC_SBRDN_AMT	Amount of expenses paid by beneficiary based on claims reviewed
	EDEC_JBRDN_AMT	Amount of expenses paid by insurer based on claims reviewed
	EDEC_CT_TOT_AMT	Total amount for CT based on claims reviewed
	EDEC_MRI_TOT_AMT	Total amount for MRI based on claims reviewed
	DMD_DRG_NO	DRG number of claim
	MPRSC_ISSUE_ADMIN_ID MPRSC_GRANT_NO	Institution identification number which issued prescriptions Prescription identification number (newly added since 2011 database)
	TOT_PRES_DD_CNT	Total days of prescription
	KEY_SEQ	Key sequence number of claim

DB (number of variables)	Variable name	Details
The medical treatment DB (called Table 30) [details of medical treatment bill]	SEQ_NO	Sequence number
	RECU_FR_DT	Date of the first treatment
	CLAUSE_CD	Code for clause
	ITEM_CD	Code for item
	DIV_TYPE_CD	Code for the type of treatment

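### The propensity score and matching name no care-setting variable, although setting can affect pneumonia capture and exacerbation class and the claims record it

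*Combined protocol and SAP*

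**What the plan says.** Section 9.7.1.1 opens the covariate list with "The model for the propensity score will to the extent possible include the following elements" and gives five elements: age and sex, socioeconomic status, history of COPD exacerbation, the Charlson index and history of asthma. Section 9.7.1 says LAMA and ICS/LABA matching "are performed by sex, age category (5 year spans above 55 years), years since diagnosis of COPD, as available in the database, and propensity score". Section 9.3.3 says "Age, sex and history of COPD exacerbation, income status(quartile) or medical health insurance are all matching factors". Section 9.12 describes the score more broadly, adding other comorbidities and drug use. None of these places names the type of institution or the department.

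The data hold this information. Section 9.6 lists "types of medical institutions (clinics/hospitals/tertiary hospitals/public health centres" among the utilization fields and residential area among the sociodemographic fields. Appendix Table 1 lists DSBJT_CD ("Medical subject code"), province and district of residence, and MPRSC_ISSUE_ADMIN_ID ("Institution identification number which issued prescriptions").

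In Section 9.3.2.1 recorded pneumonia needs a diagnosis code and, in addition, "CPT code of chest x-ray(71045-71048) or chest CT(71250,71260,71270,G0297) AND 3) prescription of antibiotics for pneumonia in Korean Guideline". The same section classes a treated flare as moderate if it was seen in an outpatient clinic and as severe if it led to an emergency visit or admission.

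After matching, covariates in the score whose standardized difference exceeds 0.1 are adjusted for (Sections 9.7, 9.7.1.1 and 9.7.2). Sections 9.7.1.1 and 9.7.2 also leave room for further adjustment but name no variable.

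**The concern.** Care setting may be linked to which drug class is started. It may also be linked to whether a suspected pneumonia is imaged, and to whether a flare is handled in clinic or in hospital. If both links exist, setting is a measured confounder that also acts on outcome capture. Two patients matched on every listed variable could still come from different settings, and their recorded pneumonias, exacerbation class, visits and costs could then differ for reasons unrelated to the drug. Treating the pair as a stratum in the Cox model does not remove this, because pairs are not formed on setting.

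The balance check may not reveal it. The rule that triggers adjustment is written for variables in the score, so an imbalance in setting would not set it off.

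**Working it through.** The plan has no figure on this point to reproduce. Its only relevant number is the minimum of 5,000 patients per arm (Section 9.5), a feasibility count with no stated event rate or effect size. Every other input below is an assumption.

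**Capture model.** Let pL and pI be the shares of LAMA and ICS/LABA patients managed in hospital. Let qh and qc be the probabilities that a pneumonia in hospital or clinic meets the recorded definition. The recorded hazard ratio (ICS/LABA versus LAMA) is then approximately the true one multiplied by

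[pI·qh + (1 − pI)·qc] / [pL·qh + (1 − pL)·qc].

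| pL / pI | qh / qc | Factor | True 1.20 reads |
|---|---|---|---|
| 0.60 / 0.50 | 0.90 / 0.75 | 0.825/0.840 = 0.982 | 1.18 |
| 0.70 / 0.50 | 0.90 / 0.60 | 0.750/0.810 = 0.926 | 1.11 |
| 0.70 / 0.40 | 0.90 / 0.50 | 0.660/0.780 = 0.846 | 1.02 |

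Reversing the mix gives the inverses: 1/0.982 = 1.02 to 1/0.846 = 1.18. If pL = pI, or if qh = qc, the factor is exactly 1.

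**Pneumonia treated outside the index setting.** Suppose only half of pneumonias are managed in the index setting, and the other half follow a common 60% hospital mix in both arms. In the middle row the common half is captured with probability 0.6 × 0.9 + 0.4 × 0.6 = 0.78. The arms become (0.75 + 0.78)/2 = 0.765 and (0.81 + 0.78)/2 = 0.795, so the factor is 0.765/0.795 = 0.96 instead of 0.93.

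**Against sampling error.** Assume 6 first pneumonias per 100 patient-years over 4 years. Events per arm are 5,000 × (1 − exp(−0.24)) = 1,067. The 95% interval half-width, ignoring the pair stratification, is exp(1.96 × √(2/1,067)) − 1 = 8.9%. The middle row's shift of 7.4% lies below this; the last row's 15.4% lies above it.

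**Against the plan's balance limit.** A 60% versus 50% hospital split has a standardized difference of 0.10/√((0.24 + 0.25)/2) = 0.20, twice the 0.1 limit. It would not trigger adjustment, because setting is not in the score.

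**The case against.** The strongest reply is that the bias is hypothetical. It needs arms that differ by setting after matching and imaging that differs by setting, and the documents show neither. Matching on exacerbation history, comorbidity, socioeconomic status and time since diagnosis may already narrow a setting gap. The index setting also need not be where a pneumonia is treated up to 11 years later. All of this stands. It limits what can be said about size, but not the case for measuring balance on a variable the study already plans to obtain.

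The plan is also not closed. The list is qualified, the open clauses allow further adjustment, Section 9.7 compares baseline characteristics in general, and detail is deferred to an SAP. A reader might infer that setting is excluded from any control, and the text does not support that. But the open clauses name no variable and so commit to nothing. Section 9.2 speaks of general practice, yet Section 9.1 covers the whole population and Section 9.6 runs from clinics to tertiary hospitals, so setting does vary.

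There are partial safeguards. The abstract plans a sub-analysis of pneumonia hospitalization and death. Section 9.7.2 specifies moderate or severe exacerbation; if the two are pooled, a flare that moves between classes still counts once. The requirement of more than 10 inhalers a year in both arms limits differences in contact. None of these balances setting between the arms.

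**Conclusion.** The omission is real: neither the score nor the matching names care setting, the data hold it, two primary outcomes can depend on it, and the automatic adjustment rule does not reach it. The defect is incomplete prespecification of a measured potential confounder.

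A reader might infer that the pneumonia hazard ratio will be biased, or biased towards no harm from ICS/LABA. The documents do not support this. Without the setting mix by arm and imaging rates by setting, size and direction are unknown. The factor of 0.85 to 0.98 rests wholly on assumed shares and capture rates, reverses if the mix reverses, and shrinks if pneumonia is often treated elsewhere. It covers capture only, not any confounding by severity that setting may carry.

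Nor can the bias be said to exceed the sampling error in general. In the middle scenario it is smaller than the confidence-interval half-width, and it is larger only towards the extreme end of the assumed range.

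**What to change.** Add to the list in Section 9.7.1.1, measured at the index prescription:

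- institution type in the four classes of Section 9.6;
- region of residence;
- prescribing department, provided that DSBJT_CD on the index-prescription claim is confirmed to give it. Appendix Table 1 labels this code as a medical subject in Table 20 and as a medical examination in Table 40.

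Include the same variables in the standardized-difference table and state that the 0.1 adjustment rule applies to them. Confirm which field supplies institution type: Section 9.6 names it, but Appendix Table 1 shows only institution identifiers.

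Exact matching on institution type is optional, for example as a sensitivity analysis. It may lose pairs, on top of the existing matching on sex, age band, years since diagnosis and the caliper.

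The cost is protocol and SAP wording plus the field check. Institution type and residential area are already among the data to be obtained. The change balances the index setting only, so it reduces but need not remove differences in capture for patients who later change institution.
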